11. CLINICAL SITE MONITORING

Clinical trial monitoring will be conducted to ensure that the rights and well-being of human subjects are protected, to verify that the reported clinical trial data are accurate, complete, and verifiable from source documents, and to verify that the conduct of the trial is in compliance with the currently approved protocol/amendment(s), with Good Clinical Practices (GCP), and with the applicable regulatory requirement(s). Both on-site and remote monitoring will be conducted.

12. STATISTICAL CONSIDERATIONS

12.1 Sample size

12.1.1 Primary Efficacy objective:

The primary efficacy endpoint is the relative duration of time where SpO₂ remains between 92 and 96% (inclusive). This will be obtained from continuously monitoring the subjects SpO₂ level throughout the study period such that at least 12 hours of monitoring data are available for each subject. The difference in the average amount of time will be the basis for the efficacy outcome comparison between the two ventilatory strategies.

To assess power for this objective the sample size calculation is based on preliminary data estimating the relative duration of time that SpO₂ remains between 92 and 96% (inclusive). To determine the noninferiority margin, the guidelines provided by FDA were followed (<http://www.fda.gov/downloads/drugs/guidancecomplianceregulatoryinformation/guidances/ucm202140.pdf>). From our preliminary data, the relative duration of time in which the SpO₂ remained between 92 and 96% in a four hour time interval for the MC group was 0.30 with 95% CI (0.23, 0.38). Following the guideline mentioned above we used half of the lower confidence bound to be the margin of non-inferiority (i.e. 0.12, which is equivalent to 7.2 minutes per hour) From our preliminary data, the SD for the MC and PCLC group was 0.33 and 0.23 respectively. Assuming a noninferiority margin of 0.12, a sample size of 91 subjects per group will achieve 80% power with a 2.5% one-sided significant level when the true difference between the group means is assumed to be zero. Allowing a 15% attrition rate for potential withdrawal of subjects the required sample size is 105 per group.

12.1.2 Primary Safety objective:

The primary safety endpoint is the relative duration of time with SpO₂ <88% over the study period. This will be observed by continuously monitoring each subject's SpO₂ level throughout the study period such that at least 12 hours of monitoring data are available for each subject. From our preliminary data the observed relative time where SpO₂ <88% was 0.004 and 0.002 for the MC and PCLC group respectively. The proposed sample size of 105 per group will allow us to conclude non-inferiority with a margin of 0.004 (which is equivalent to 15 seconds/hr) with 95% power with a 2.5% one-sided significant level.

Therefore for this study we are proposing to enroll a total of 210 subjects to test the noninferiority hypothesis for both our primary safety and effectiveness outcomes. For all sample size estimates, PASS version 12 (PASS, NCSS LLC., Utah, US) was used.

If noninferiority is demonstrated, the proposed sample size also has 80% power to test for the superiority of the LLC group versus MC group both in terms of the primary effectiveness and safety outcomes if the true difference between ventilatory strategies is at least 0.14 (which is equivalent to 8.2 minute per hour) for the primary efficacy endpoint and is at least 0.003 (which is equivalent to 10 second per hour) for the primary safety endpoint.

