5.2 Sample size

The target sample size is 105 subjects per study arm for a total of 210 subjects. The detail of the sample size estimation is given in section 12.

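### Section 12.1.1: 105 per group preserves 91 evaluable subjects only up to about 13% attrition, not the stated 15%, although power at 15% loss is still about 80%

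*Combined protocol and SAP*

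**What the plan says.** Section 12.1.1 sizes the trial on non-inferiority for the share of time that SpO2 is in the target range. Its inputs are:

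- margin: "Assuming a noninferiority margin of 0.12"
- variability, from preliminary data: "the SD for the MC and PCLC group was 0.33 and 0.23 respectively"
- error rate and assumed effect: "with a 2.5% one-sided significant level when the true difference between the group means is assumed to be zero"

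From these it concludes that "a sample size of 91 subjects per group will achieve 80% power". The next step is the attrition allowance: "Allowing a 15% attrition rate for potential withdrawal of subjects the required sample size is 105 per group". Section 5.2 carries the result forward ("The target sample size is 105 subjects per study arm for a total of 210 subjects"), and the closing paragraphs of section 12.1 repeat the total of 210. The formula that takes 91 to 105 is not shown. The software is named (PASS version 12), but the procedure within it is not.

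Section 12.2 bears on who would be lost. The intent-to-treat set contains everyone who was randomized and began the assigned strategy, and the outcome is scored against the time actually monitored.

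**The concern.** A withdrawal rate is a fraction of the subjects enrolled. The enrolled number must therefore be the evaluable number divided by one minus that rate. Multiplying the evaluable number by one plus the rate gives too few, and the stated 105 is what that multiplication yields.

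Non-inferiority on effectiveness is one of the two conditions for study success in the Protocol Summary, so its sample-size statement should be reproducible from its own figures. As written, a reader who applies 15% loss to 105 arrives below the 91 that the plan says it needs. What is at stake is the accuracy of the stated allowance and, at most, a very small amount of power.

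**Working it through.** **Inputs.** All come from section 12.1.1: margin d = 0.12; SDs 0.33 (manual control) and 0.23 (closed loop); one-sided alpha 0.025; power 0.80; true difference 0; 91 per group before attrition; attrition 15%; 105 per group after. Allocation is equal (section 5.6.1).

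**Step 1: the base of 91.** With the normal approximation,

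n = (s1² + s2²)(z0.975 + z0.80)² / d² = (0.1089 + 0.0529) x (1.960 + 0.842)² / 0.0144 = 88.19, so 89 per group.

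With the noncentral t distribution the requirement is 90. The stated 91 is therefore reproduced to within one or two subjects and is slightly generous.

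**Step 2: the inflation.**

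- Multiplying: 91 x 1.15 = 104.65, which rounds up to 105. This matches the plan.
- Dividing: 91 / (1 - 0.15) = 107.06, which rounds up to 108 per group, or 216 in total. As a check, 108 x 0.85 = 91.8, while 107 x 0.85 = 90.95 just misses.

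The difference is 3 per group and 6 in total.

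**Step 3: what 105 covers.** The largest loss that leaves 91 is 1 - 91/105 = 14/105 = 13.3%. At 15% loss, 105 x 0.85 = 89.25, so about 89 per group remain, 2 short of 91.

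**Step 4: power at those sizes.** The standard error is √((0.33² + 0.23²)/n). The normal approximation gives power Φ(d/SE - 1.960). The t version uses noncentrality d/SE with Welch degrees of freedom. At n = 89, SE = √(0.1618/89) = 0.0426 and d/SE = 2.814. The normal approximation then gives Φ(0.854) = 80.4%.

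| n per group | Power, t (Welch) | Power, normal |
|---|---|---|
| 89 (105 less 15%) | 79.9% | 80.4% |
| 90 | 80.3% | 80.8% |
| 91 (stated base) | 80.8% | 81.2% |
| 105 (no loss) | 86.0% | 86.4% |
| 108 (no loss) | 87.0% | 87.3% |

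The pooled-variance t test also gives 79.9% at 89. Going from 91 to 89 costs about 0.9 percentage points by either method.

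**The case against.** Four points can be made for the plan.

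**Power survives.** A reader might infer that the trial is underpowered, or that its power drops below the stated 80%. The documents do not support that. At 89 per group the result rounds to 80% under each method. Whether it lies just above or just below depends on using a normal or a t calculation, and the plan does not say which was used. The reason is that 91 already exceeds the 89 or 90 that 80% power requires. This objection stands in full.

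**The formula is not printed.** A reader might also state as fact that the planners multiplied by 1.15. The match with 104.65 makes that the likeliest explanation, but it is an inference. A base of 89 gives 89/0.85 = 104.7, which also rounds up to 105. If 89 was the base, the division was correct and the printed 91 is the figure out of line. Either way the sentence does not hold together as written, and the 13.3% figure does not depend on how 105 was reached.

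**Not every withdrawal is a lost subject.** Section 12.2 keeps anyone who started the assigned strategy and normalizes to the monitoring time available. It extends monitoring to reach 12 evaluable hours, scores subjects who die on the time observed, and expects few missing data. Loss from the primary analysis may well be below 15%. This softens the consequence but does not correct the stated allowance. Losses would also count in full in the planned sensitivity analysis that leaves out subjects without 12 hours of monitoring. In addition, section 3.3 says that data will not be used where FiO2 cannot be brought down from 1.0.

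**The gap is small.** Three per group is under 3%. That is fair as to importance, but rounding does not turn 107.06 into 105.

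**Conclusion.** The point holds as a minor arithmetic correction. From the stated base of 91, an allowance for 15% attrition requires 108 per group; 105 gives an allowance of about 13%. This follows from the plan's own three figures and assumes only that attrition is a fraction of those enrolled.

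The practical effect is very small: at a true 15% loss, about 89 per group and power of about 80%. The power figures rest on the plan's margin, SDs and zero true difference, and on the pessimistic assumption that every withdrawn subject contributes nothing. The finding gives no ground for changing the enrolment target, the margin or the analysis.

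**What to change.** Keep 210 subjects. Reword the attrition sentence in section 12.1.1 along these lines: *105 per group preserves 91 evaluable subjects with up to about 13% attrition; at 15% attrition about 89 per group remain, with power of about 80%.* A power figure to one decimal place is best avoided unless the PASS procedure is also named, because the t and normal results fall on either side of 80%. If the planners did inflate from a base other than 91, the base should be corrected in the same sentence.

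Section 5.2 and the total in section 12.1 need no change. The cost is one sentence and no extra subjects; the stated allowance becomes slightly less favourable. Raising enrolment to 108 per group would also reconcile the figures, but it would add 6 subjects for a gain in power of about one percentage point, which is not worth asking for.

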1. PROTOCOL SUMMARY

Title:

FiO₂ Closed-Loop Control Using the ZOLL 731 Series Ventilator.

Précis:

A randomized, multicenter trial involving critically-ill patients comparing conventional, manual control of inspired oxygen (FiO₂) within a target range, with a computer-controlled, closed-loop FiO₂ delivery using an FDA-cleared continuous ventilator.

Objectives:

The objective of this study is to demonstrate that physiologic closed-loop control (PCLC) is at least as safe and effective as manual control in keeping hemoglobin oxygen saturation (SpO₂) within the target range of 92 to 96%.

The primary efficacy outcome is the relative duration as defined by the total duration of minutes with SpO₂ within the target range of 92 to 96% divided by 720 minutes (the planned duration of the study). Similarly the relative duration for the primary safety outcome is defined as the total duration of time that the SpO₂ level at or above 88% divided by 720 minutes.

Hypothesis:

We plan to conduct a 2-state statistical test: non-inferiority followed by a superiority test. Demonstration of non-inferiority for both the effectiveness and safety endpoints is required for study success.

Primary effectiveness for non-inferiority: The use of PCLC to maintain oxygen saturation (SpO₂) within the target range of 92 to 96%, as measured by the relative duration, is not inferior to the manual control (MC).

Secondary effectiveness for non-inferiority: The use of PCLC to maintain oxygen saturation (SpO₂) within the target range of 92 to 96% when FiO₂ > 21% and SpO₂ ≥ 92% when FiO₂ = 21%, as measured by the relative duration, is not inferior to the manual control (MC) group.

Primary effectiveness for superiority: The relative duration of time with SpO₂ within the target range of 92 to 96% is greater in the PCLC compared with manual control (MC) group.

Secondary effectiveness for superiority: The relative duration of time with SpO₂ within the target range of 92 to 96% when FiO₂ > 21% and

SpO₂ ≥ 92% when FiO₂ = 21%, as measured by the relative duration, is greater in the PCLC compared with manual control (MC) group.

[figure not shown]
Primary safety: The use of PCLC to maintain the SpO₂ level at or above 88%, as measured by relative duration of time, is not inferior to the manual control (MC).

Population:

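### The two co-primary powers in section 12.1 rest on different sample sizes, and the power to meet both, which study success requires, is not stated

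*Combined protocol and SAP*

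**What the plan says.** Section 1 (Protocol Summary, Hypothesis) sets the success rule: "Demonstration of non-inferiority for both the effectiveness and safety endpoints is required for study success".

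Section 12.1.1 sizes the efficacy test. The inputs are "Assuming a noninferiority margin of 0.12" and the statement that "the SD for the MC and PCLC group was 0.33 and 0.23 respectively". The result, for which the plan takes the two arms to have equal means, is given in these words: "a sample size of 91 subjects per group will achieve 80% power with a 2.5% one-sided significant level when the true difference between". Attrition is then added: "Allowing a 15% attrition rate for potential withdrawal of subjects the required sample size is 105 per group".

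Section 12.1.2 covers the safety test: "The proposed sample size of 105 per group will allow us to conclude non-inferiority with a margin of 0.004". The claim for that number and margin is made "with 95% power with a 2.5% one-sided significant level". The only planning data given there are the means: "the observed relative time where SpO₂ <88% was 0.004 and 0.002 for the MC and PCLC group respectively". It gives no standard deviation and no assumed true difference. The closing text of section 12.1 applies the same 210 subjects to both hypotheses. Section 12.1 gives neither a joint power nor a correlation between the endpoints.

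**The concern.** Both endpoints come from the same SpO₂ recording in the same subjects, so a subject lost to one is lost to the other. Yet the efficacy power is quoted at the number left after attrition, and the safety power at the number enrolled. One evaluable number cannot support both statements.

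The success criterion is also a conjunction, so its power cannot exceed the smaller of the two single-endpoint powers and is usually below it. A sponsor or DSMB member who reads 80% and 95% may take 80% as the chance of success when there is truly no efficacy difference. On the plan's own attrition it is lower than that for most plausible correlations. What is at stake is how the design is described. Neither the validity of the tests nor subject safety is affected.

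**Working it through.** **Inputs.** Efficacy (12.1.1): margin 0.12, SDs 0.33 and 0.23, one-sided 2.5%, true difference 0, 91 per group, 15% attrition. Safety (12.1.2): margin 0.004, one-sided 2.5%, 95% power at 105 per group. The correlation between the two tests is not in the documents, so a range is shown.

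**1. Reproduce the efficacy figure.** n = (0.33² + 0.23²)(1.960 + 0.842)² / 0.12² = 0.1618 × 7.849 / 0.0144 = 88.2, so 89 per group by the normal approximation. The unequal-variance t calculation gives 90. The stated 91 agrees closely.

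**2. Evaluable number.** 91 × 1.15 = 104.65, rounded to 105. Losing 15% of 105 leaves 105 × 0.85 = 89.25, so 89. (Dividing, 91/0.85 = 107.1, would call for 108.) The plan's evaluable number is therefore 89 to 91 per group.

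**3. Efficacy power.** Power = Φ(0.12/√(0.1618/n) − 1.960).
- n = 89: Φ(2.814 − 1.960) = 80.4%
- n = 91: Φ(2.846 − 1.960) = 81.2%
- n = 105: Φ(3.057 − 1.960) = 86.4%

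**4. Safety power.** No SD is given, so the 95% cannot be checked directly, but it can be rescaled. Power of 95% at 105 means that (margin + true advantage)/SE = 1.960 + 1.645 = 3.605. The SE varies as 1/√n, so power at n is Φ(3.605·√(n/105) − 1.960), whatever SD and true difference were assumed.
- n = 89: Φ(3.605 × 0.9207 − 1.960) = Φ(1.359) = 91.3%
- n = 91: Φ(3.605 × 0.9309 − 1.960) = Φ(1.396) = 91.9%

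**5. Power to meet both criteria.** This is the product under independence, and the bivariate normal probability otherwise. The ceiling is the smaller single-endpoint power.

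| Analysed per group | Efficacy | Safety | Independent | Correlation 0.5 | Correlation 0.8 | Ceiling |
|---|---|---|---|---|---|---|
| 89 | 80.4% | 91.3% | 73.4% | 76.2% | 78.7% | 80.4% |
| 91 | 81.2% | 91.9% | 74.6% | 77.3% | 79.7% | 81.2% |
| 105 | 86.4% | 95.0% | 82.0% | 83.7% | 85.4% | 86.4% |

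**6. Sensitivity to the safety inputs.** Section 3.2.2 reports 1.25 ± 2.64 and 0.55 ± 1.37 minutes below 88% in 4-hour periods. Assume that the ± values are SDs and carry over to this design: 2.64/240 = 0.0110 and 1.37/240 = 0.0057. With a true safety difference of zero, safety power at 89-91 is 86-87% and joint power under independence is 69-71%. With a 0.002 advantage for closed-loop control, safety power exceeds 99% and joint power is 80-81%. The answer depends heavily on an assumption that section 12.1.2 does not state.

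**The case against.** The strongest reply is that the 15% is a cautious allowance and that few subjects will drop out of the analysis. Section 12.2 keeps everyone who was randomized and started the assigned strategy. It uses a proportion of actual monitoring time, extends monitoring to reach 12 evaluable hours, uses the observed time of subjects who die, and expects little missing data. On that reading 105 is the right number for safety, and joint power is about 82% under independence. This stands as a reason to state joint power conditionally. It does not reconcile section 12.1: if attrition does not reduce the analysed number, the efficacy power is the one quoted on the wrong basis, and it should read about 86%. Some loss is also foreseen, since section 3.3 sets aside data where FiO₂ cannot be brought down from 1.0, without giving a rate.

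A second reply is that zero efficacy difference is conservative, because the earlier trial in section 3.2.2 favoured automated control. That is fair. At 89-91 per group under independence, a true advantage of 0.02 gives joint power of 83-84%. The plan nevertheless chose zero as its planning value, and the stated 80% rests on it.

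A reader might also infer three stronger claims, which the documents do not support:
- **That power for success is simply 73-76%.** The figure depends on independence and on full attrition. Its upper end, 0.80 × 0.95 = 76%, multiplies powers taken at two different sample sizes.
- **That it is really about 69-70%.** This needs the crossover SDs of section 3.2.2 together with a zero safety difference, which section 12.1.2 does not state.
- **That joint power must fall below both stated figures.** With all 105 analysed it is about 82%, above the stated 80%.

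**Conclusion.** The point holds as an inconsistency and an omission in how power is reported. The efficacy calculation reproduces, and no stated figure is shown to be miscalculated on its own basis. On the plan's 15% attrition, however, the quoted 95% safety power is about 91-92%; this holds whatever SD and true difference lay behind the 95%.

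Power for the success criterion at 89-91 per group is about 73-75% with independent endpoints, 76-77% at correlation 0.5, and no more than about 80-81% however strong the positive correlation. It is about 82% or more only if all 105 per group are analysed. These figures assume a true efficacy difference of zero and accept the stated safety power, which cannot be verified from section 12.1. The matter is minor: it changes what the sponsor and DSMB are told, and nothing in the conduct or analysis of the trial.

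**What to change.** In section 12.1.2, restate safety power at the same evaluable number as efficacy (about 91-92% at 89-91 per group), and give the SD and true difference used so that it can be checked. Then add the joint power as a conditional range, for example: with a true efficacy difference of zero, power to meet both co-primary criteria at 89-91 evaluable per group is about 73-75% if the endpoints are independent, 76-77% at correlation 0.5 and at most about 80-81%; it is about 82% or more if all 105 per group are analysed. A single figure without conditions should not be used.

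If the sponsor expects the intention-to-treat rules to keep nearly everyone in the analysis, section 12.1 should say so and quote both powers at 105. Either basis is acceptable if it is applied to both endpoints.

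The change is a few sentences. It requires no change in sample size, and its only cost is a slightly less favourable stated power.

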12.2 Statistical Analysis

For the primary outcomes, the intent-to-treat (ITT) population will be used for all efficacy and safety analyses. All subjects that were randomized and started the assigned ventilation strategy protocol will be included in the ITT. All summary tables for quantitative parameters will display mean, standard deviation, median, interquartile range, and range (minimum and maximum), as well as number of missing data (if relevant). All summary tables for qualitative parameters will display counts, percentages and number of missing data if relevant. Baseline characteristics will be described using the ITT population. Demographics, medical history and other baseline variables will be summarized as appropriate to the type of data. The primary effectiveness outcome will be defined as the proportion of time during the 12 hour monitoring period that the subject's SpO₂ levels were within the target range relative to the actual total monitoring time (which is targeted to be 12 hours for all subjects). By using the proportion of time instead of the actual time, we are able to normalize the outcome based on the total amount of monitoring time available. We will assess normality of the response variables within each of the two groups by visual inspection of the histograms and box plots and by performing the test for normality of data using the Shapiro Wilk test. If the assumption of normality for the primary effectiveness outcome does not seem tenable, we will use the arcsine square root transformation which is recommended to normalize skewed percentage data. A one-sided lower 97.5% confidence interval will be calculated for the difference between the two monitoring strategy groups (PCLC minus MC) in terms of the effectiveness outcome (duration where SpO₂ remains between 92 and 96% relative to the total monitoring time) and the lower limit will be compared to the noninferiority margin of 0.12. Similar analyses will be conducted for the secondary effectiveness outcome with the only difference being the way the duration is calculated for the secondary effectiveness outcome. For this analysis, the target duration will be calculated as amount of time that SpO₂ remains between 92 and 96% when FiO₂ > 21% and SpO₂ ≥ 92% when FiO₂ = 21%. The safety outcome (duration where SpO₂ remains above 88% relative to the total monitoring time) will be assessed using a one-sided lower 97.5% confidence interval and the lower limit will be compared to the non-inferiority margin of 0.004. If non-inferiority is established for an endpoint, we will proceed in conducting a superiority test and will compare the lower confidence limit to 0.

For the analysis of secondary safety outcome, data point estimates will be reported with 95% confidence intervals followed by a Fisher's Exact Test at the 5% level of confidence. Specifically the percentage of subjects reporting at least one adverse event (i.e serious, any device related, etc.) will be calculated for each group and compared using Fisher's Exact Test. The relative risk of each adverse event with the corresponding two-sided 95% confidence interval will be presented.

Missing data: The primary analysis is an intent to treat analysis. In order to minimize the possibility of missing data, the total duration of monitoring will be extended for each subject as needed in order to collect at least 12 hours of evaluable data. As a sensitivity analysis, the primary outcome measure also will be calculated as the relative time the subject was on target compared to the total amount of time they were on manual or closed-loop control. Therefore each subject should have the outcome measurement. The amount of missing data is expected

to be low based on past experience with subject retention. However there is a very low probability that some subjects may die before completing 12 hours of monitoring on the device. In this case, the relative duration will be derived by using the total duration of time the subject was on target relative to the monitoring time until they died. If a subject does not have 12 hours of monitoring data on the device due to a reason other than death, we will conduct sensitivity analysis by assuming different scenarios. In a worst case scenario, the primary outcome will be computed as the total time in the target range divided by 720 minutes. In a best case scenario, the primary outcome will be computed as the total time in the target range divided by the total amount of time the subject was observed (i.e. <720 minutes). In the event of missing data on the primary safety and efficacy outcomes (except where the subject died), the reason for the missing values will be explored, and the pattern of missing values (e.g. missing at random, missing completely at random) will be evaluated. In addition, analyses excluding those subjects without 12 hours of monitoring will also be conducted as sensitivity analyses.

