4.3 Study Design

- The trial will employ a two group parallel design in which subjects will be randomized to one of the two ventilatory strategies for a 12 hour period. Twelve hours was selected because it captures most scenarios where mechanical ventilation could be required in the prehospital and transport environments in both military and civilian use. The two ventilatory strategies are: 1) manual adjustment of the ventilator FiO₂ by the treatment team based on physician order or according to current protocol (manual control period) or 2) automatic adjustment by the system algorithm (closed-loop period). Manual adjustment will use the same SpO₂ target (94%) as the closed loop system. During closed-loop control, the FiO₂ can be overridden by the clinician at any time.
- This is a multicenter trial with four sites (The University of Cincinnati Level 1 Trauma Center, The Los Angeles County Medical Center Level 1 Trauma Center, The University of Texas Health Science Center at Houston Level 1 Trauma Center, and Regions Hospital Level 1 Trauma Center). All patients age 18 to 65 inclusive admitted to the Trauma/Acute Care service and requiring invasive mechanical ventilation will be screened for the study. This age range is intended to represent the group of warfighters and support personnel to be treated with this system. These patients will be unable to provide consent due to the severity of their injuries. Their legal representative will be approached as soon as possible. Once consent has been obtained the patient will be randomly assigned to one of the two study arms and enrolled in the study; subjects are not considered to be enrolled in the study until they have been successfully randomized to receive either CLC or manual control of the study ventilator.
- Baseline characteristics including demographic information, anatomic Injury Severity Score (ISS), physical exam findings, and physiologic (APACHE II) markers of disease severity, and admitting diagnoses will be assessed for all subjects. An arterial blood gas obtained prior to study enrollment will be recorded to define the degree of lung injury. Ventilator settings and vital signs immediately prior to the start of the clinical study will also be recorded.

Subjects will be studied for a total of 12 hours and will be monitored for an additional 24 hours

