The closed-loop control system includes both audible and visual alarms to alert the clinician of an unreliable signal from the pulse oximeter, malposition of the pulse oximeter sensor, and subject SpO₂ less than 88%. Details of these alarms are documented in Appendix B which is taken from the Operation Manual. All alarms and low SpO₂ conditions will be recorded automatically on the laptop computer data logger.

If the subject requires a procedure in the ICU that the standard of care requires an increase in FiO₂ to 1.0 (e.g. bronchoscopy) the data collection will automatically continue but such data will

not be considered in the statistical analysis because such procedures are not part of the trial protocol. The Case Report Form will capture such events and note the times that such procedures began and were completed. Data inclusion in the statistical analysis will resume once FiO₂ control returns to the trial protocol. If the subject requires transfer to the operating room, radiology for treatment or some other non-ICU location, data collection will not be included in the statistical analysis until the subject returns to the ICU. These incidents outside of the ICU will also be captured on the Case Report Form. The goal of the study will be to have a minimum of 12 hours of data collection for each subject in either arm of the study

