5.5 Strategies for Recruitment and Retention

There will be no compensation to subjects for study participation.

We anticipate subject participation not to exceed 24 hours of data collection (to produce 12 hours of evaluable data) for the entire study; however subjects will be monitored for adverse events for 24 hours following the end of the intervention. Subjects will be terminated from the study after the 24 hour period ends.

We have chosen the four Level 1 trauma units to maximize recruitment of a study population that meets all of the inclusion criteria. Each trauma unit admits approximately 85 trauma patients/year that would be eligible for this study and we plan to recruit equal numbers of subjects from each trauma unit. If this is not feasible, no more than 60% of the total subjects will come from a single study site.

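### The Protocol Summary divides both co-primary outcomes by a fixed 720 minutes, which conflicts with section 12.2 and counts a short record's missing time as time below 88%

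*Combined protocol and SAP*

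**What the plan says.** **Protocol Summary, Objectives.** The efficacy outcome is the "total duration of minutes with SpO₂ within the target range of 92 to 96% divided by 720 minutes (the planned duration of the study". The safety outcome is "the total duration of time that the SpO₂ level at or above 88% divided by 720 minutes". Non-inferiority on both is required for success.

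**Section 12.2.** Effectiveness is time in range "relative to the actual total monitoring time (which is targeted to be 12 hours for all subjects". The reason given is that "we are able to normalize the outcome based on the total amount of monitoring time available". Safety is the "duration where SpO₂ remains above 88% relative to the total monitoring time". Every subject who was randomized and started the assigned strategy stays in the ITT population.

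**Section 12.2, Missing data.** A subject who dies early is scored on monitoring time until death. For other short records there are two sensitivity scenarios: division by 720 (worst case) and by observed time (best case). Both are worded for time in the target range only.

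**Record length.** Section 4.3 says "Subjects will be studied for a total of 12 hours" and also aims for "a minimum of 12 hours of data collection for each subject in either arm of the study". Section 5.5 says "We anticipate subject participation not to exceed 24 hours of data collection (to produce 12 hours of evaluable data) for the entire study". Section 4.3 removes certain procedures and time outside the ICU from the analysis. Section 5.6.2 allows withdrawal and termination, and section 12.1.1 allows 15% attrition.

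**The concern.** Both definitions are current text and both describe the primary analysis. They agree at 720 evaluable minutes and otherwise differ by the factor L/720, where L is the evaluable record length. (They also agree if the numerator is zero, which is possible for efficacy but hardly for safety.)

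Short records are foreseeable and stay in the analysis. Dividing a short record by 720 treats every unobserved minute as out of range for efficacy and as below 88% for safety. Efficacy can absorb this, because its margin is 0.12. Safety scores lie near 1 and the margin is 0.004, so a few short records in one arm could decide the safety conclusion for reasons unrelated to oxygenation. A programmer working from the Summary and one working from section 12.2 would report different primary results.

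**Working it through.** **Inputs.** Margins 0.12 and 0.004, and 105 per arm (section 12.1). Manual-control (MC) proportion in range 0.30 (section 12.1.1). Proportion of time below 88%: 0.004 MC and 0.002 PCLC (section 12.1.2), so 0.996 and 0.998 at or above 88%. The documents give no distribution of record length, so 600, 540 and 360 minutes below are assumptions.

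**The plan's own figures.** 0.004 × 3600 = 14.4 seconds per hour, which the plan rounds to 15. Over 12 hours the safety margin is 0.004 × 720 = 2.88 minutes. The efficacy sample size also reproduces: (0.33² + 0.23²) × (1.960 + 0.842)² / 0.12² = 88.2, so 89 per group by the normal formula against the stated 91. A noncentral-t calculation with unequal variances gives 80.8% power at 91. The sample size does not depend on the present point.

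**Score for one subject** with constant proportion p:
- Protocol Summary: p × L/720
- Section 12.2: p

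**Shift in the arm mean** from one short record among 105: p × (L/720 − 1)/105.

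| Endpoint, p | L (min) | Summary score | Section 12.2 score | Shift in arm mean | Share of margin |
|---|---|---|---|---|---|
| Safety, 0.996 | 600 | 0.830 | 0.996 | −0.0016 | 40% |
| Safety, 0.996 | 360 | 0.498 | 0.996 | −0.0047 | 119% |
| Efficacy, 0.30 | 600 | 0.250 | 0.300 | −0.0005 | 0.4% |
| Efficacy, 0.30 | 360 | 0.150 | 0.300 | −0.0014 | 1.2% |

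**Could the safety verdict change?** This needs SDs. Section 3.2.2 reports 2.64 and 1.37 minutes below 88% in 4-hour periods, so 2.64/240 = 0.0110 (MC) and 1.37/240 = 0.0057 (PCLC). Carrying these to 12 hours is a further assumption. One PCLC record shifted by δ = 0.998 × (L/720 − 1) moves the arm mean by δ/105 and adds δ²/105 to that arm's variance. The lower limit is the difference minus 1.96 SE.
- All records 720 minutes: difference 0.0020, SE 0.0012, limit −0.0004. Non-inferior.
- One PCLC record of 600 minutes (δ = −0.166): difference 0.0004, SE 0.0020, limit −0.0035. Still non-inferior.
- One PCLC record of 540 minutes (δ = −0.2495): difference −0.0004, SE 0.0027, limit −0.0056. Fails.

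Under section 12.2 scoring, short length alone changes none of these.

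**A consistency check.** Sections 4.1.3, 9.1.1 and 12.1.2 state safety as time below 88%, while the Summary uses time at or above it. Over observed time these are complements. Over 720 they are not: a 600-minute record at 0.996 scores 0.830 at or above 88% and 0.004 × 600/720 = 0.0033 below, which together make 0.833. The unobserved sixth counts as hypoxemia in one form and as safe time in the other.

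**The case against.** The strongest reply is that the primary denominator can already be determined. Section 12.2 is the operative text. It gives the denominator for both endpoints and a reason for it, while the Summary's 720 is glossed as the planned duration. The treatment of deaths agrees with section 12.2, and division by 720 appears there only as a worst case. This stands, and it shows which text to correct. It does not remove the contradiction: the Summary states a computable rule for both outcomes, and the missing-data paragraph does not say which denominator is primary for a short record that did not end in death.

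It is also fair that the record lengths above are assumed, that the plan extends monitoring to replace excluded time, and that it expects little missing data. The figures show sensitivity and are not a forecast.

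A reader might go further and infer that records longer than 720 minutes are a second serious problem, since a 723-minute record at 0.996 scores 0.996 × 723/720 = 1.0002 under the Summary, a shift the size of the margin. The documents do not support that weight. Section 12.2 places the proportion within the 12-hour monitoring period, and sections 4.3 and 5.5 point to a 12-hour window, although none is a formal cut rule. The margin applies to the arm difference, and one such subject moves the arm mean by 0.00415/105 = 0.00004, about 1% of it. Whole-record scoring under section 12.2 cannot exceed 1.

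**Conclusion.** The point holds as a minor inconsistency with a clear resolution: the fixed 720-minute denominator in the Protocol Summary is wrong as written, and section 12.2 should govern. It matters for short records and essentially for safety, where one non-death record of 600 minutes among 105 is worth 40% of the margin and one of 360 minutes 119%. Efficacy moves by about 1% of its margin or less in the same cases.

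These sizes rest on assumed record lengths, on a constant proportion within each record, and on the Summary rule being the one applied. The reversal with one 540-minute PCLC record also rests on SDs borrowed from 4-hour crossover periods. Nothing here suggests that an analysis run under section 12.2 would be biased by the choice of denominator, or that the sample size needs to change.

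**What to change.** 1. In the Protocol Summary, for both co-primary outcomes, replace division by 720 minutes with division by the subject's evaluable monitoring time (planned 720 minutes).
2. In the missing-data paragraph of section 12.2, state that observed evaluable time is the primary denominator for short records, for effectiveness and safety alike. Keep division by 720 only as the worst-case sensitivity analysis.
3. Optionally, state that scoring uses the first 720 evaluable minutes. Under section 12.2 scoring this has little effect.

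The first two are wording changes with no effect on the sample size. The third adds one truncation step to the analysis program and leaves minutes beyond 720 unused.
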